10.1 Study Visit Windows

Study visit windows will be used to map visits using study day intervals. Observations at each scheduled visit and Early Termination will be assigned to Week 2, Week 4, Week 8 and Week 12 visits based on their visit windows as shown in [Table 10.1A](#). This visit window convention applies to tables and listings for all efficacy and safety scales (CC1 [REDACTED])

CCI

SAS, AIMS and BARS). This derived study window variable will be named as DAY and will be footnoted. In listings, it will be listed along with the CRF study visit.

Table 10.1A shows classifications for study day intervals in the open-label treatment phase. The variable “target day” is defined using the number of days since the start of open-label brexpiprazole dosing. The first day of open-label brexpiprazole dosing is defined as “Day 1”.

If more than one observation falls within a particular study day interval, then the last observation within that interval is used. Evaluations occurring more than 7 days after the last open-label brexpiprazole dosing date will not be mapped into study visit windows, and will be excluded from the analysis.

Table 10.1A: Study Day and Visit Windows in the Open-label Treatment Phase

Week	Target Day ^a	Study Day Interval ^a
2	14	2-21
4	28	22-42
8	56	43-70
12	84	71-91 ^b

^a Relative to the first day of open-label brexpiprazole in the open-label treatment phase.

^b Evaluations occurring more than seven days after the last dosing date of open-label brexpiprazole in the open-label treatment phase will be excluded from the efficacy analyses.

[figure not shown]
10.2 Scales: Rules for Scoring and Handling of Missing Data

CCI

[figure not shown]
CCI

CCI

[figure not shown]
CCI

CCI

[figure not shown]
CCI

CCI

CCI

10.2.9 SAS

The SAS will be used to evaluate extrapyramidal symptoms (EPS). It consists of a list of 10 symptoms of Parkinsonism (gait, arm dropping, shoulder shaking, elbow rigidity, wrist rigidity, head rotation, glabella tap, tremor, salivation, and akathisia). Each item will be rated on a 5-point scale, with a score of zero representing absence of symptoms, and a score of 4

representing a severe condition. The SAS Total score is the sum of ratings for all 10 items, with possible Total scores from 0 to 40. The SAS Total score will be un-evaluable if less than 8 of the 10 items are recorded. If 8 or 9 of the 10 items are recorded, the Total score will be the mean of the recorded items multiplied by 10 and then rounded to the first decimal place.

10.2.10 AIMS

The AIMS is a 12-item scale. The first 10 items are rated from 0 to 4 (0=best, 4=worst). An item score of 0, depending on the item, either means: no abnormal involuntary movement (AIM), or no incapacitation due to AIM, or no awareness of AIM. An item score of 4 either means: severe AIM, or severe incapacitation due to AIM, or being aware of, and severe distress caused by AIM. Items 11 and 12, related to dental status, have dichotomous responses, 0=no and 1=yes. The AIMS Total Score is the sum of the ratings for the first seven items. The possible total scores are from 0 to 28. The AIMS Total Score will be un-evaluable if less than 6 of the first 7 items are recorded. If 6 of the items are recorded, then the total score will be the mean of the recorded items multiplied by 7 and then rounded to the first decimal place.

10.2.11 BARS

The BARS consists of 4 items related to akathisia: objective observation of akathisia by the investigator, subjective feelings of restlessness by the subject, subjective distress due to akathisia, and global clinical assessment of akathisia. The first 3 items will be rated on a 4-point scale, with a score of zero representing absence of symptoms and a score of 3 representing a severe condition. The global clinical evaluation will be made on a 6-point scale, with zero representing absence of symptoms and a score of 5 representing severe akathisia.

10.2.12 C-SSRS

Suicidality will be monitored during the trial using the C-SSRS. The “Since Last Visit” version of the scale will be completed at all visits for all subjects. Any subject with active suicidal ideation and intent at entry or who has engaged in prohibited suicidal behaviors, or who, in the clinical judgment of the investigator, presents a serious risk of suicide should be excluded from the trial.

11 Potential Clinical Relevance Criteria from Protocol

Appendix 1 Criteria for Identifying Vital Signs of Potential Clinical Relevance

Variable	Criterion Value ^a	Change Relative to Baseline ^a
Heart Rate ^b	> 120 bpm < 50 bpm	≥ 15 bpm increase ≥ 15 bpm decrease
Systolic Blood Pressure ^b	> 180 mmHg < 90 mmHg	≥ 20 mmHg increase ≥ 20 mmHg decrease
Diastolic Blood Pressure ^b	> 105 mmHg < 50 mmHg	≥ 15 mmHg increase ≥ 15 mmHg decrease
Orthostatic Hypotension	≥ 20 mmHg decrease in systolic blood pressure and a ≥ 25 bpm increase in heart rate from supine to sitting/standing	Not Applicable (baseline status not considered)
Weight	-	≥ 7% increase ≥ 7% decrease

^a In order to be identified as potentially clinically relevant, an on-treatment value must meet the “Criterion Value” and also represent a change from the subject’s baseline value of at least the magnitude shown in the “Change Relative to Baseline” column.

^b As defined in “Supplementary Suggestions for Preparing an Integrated Summary of Safety Information in an Original NDA Submission and for Organizing Information in Periodic Safety Updates,” FDA Division of Neuropharmacological Drug Products draft (2/27/87).

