10.6 Appendix 6: Criteria for Identifying Vital Signs of Potential Clinical Relevance

Variable	Criterion Value ^a	Change Relative to Baseline ^a
Heart rate ^b	> 100 bpm < 50 bpm	≥ 10 bpm increase ≥ 10 bpm decrease
Systolic blood pressure ^b	≥ 140 mmHg Supine < 90 mmHg	≥ 20 mmHg increase ≥ 20 mmHg decrease
Diastolic blood pressure ^b	≥ 90 mmHg Supine < 60 mmHg	≥ 10 mmHg increase ≥ 10 mmHg decrease
Orthostatic hypotension	≥ 30 mmHg decrease in systolic blood pressure and/or a decrease of ≥ 20 mmHg in diastolic blood pressure after at least 3 minutes of standing compared to the previous supine blood pressure.	Not applicable (baseline status not considered)
Orthostatic tachycardia	≥ 25 bpm increase in heart rate from supine to standing	Not applicable (baseline status not considered)
Weight	—	≥ 7% increase ≥ 7% decrease

bpm = beats per minute.

^aIn order to be identified as potentially clinically relevant, an on-treatment value must meet the “Criterion Value” and also represent a change from the subject’s baseline value of at least the magnitude shown in the “Change Relative to Baseline” column.

^bAs defined in “Supplementary Suggestions for Preparing an Integrated Summary of Safety Information in an Original New Drug Application Submission and for Organizing Information in Periodic Safety Updates,” FDA Division of Neuropharmacological Drug Products draft (2/27/87).

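### SAP Section 11 presents its vital-sign criteria as the protocol's, but 8 of the 12 heart-rate and blood-pressure limits differ, orthostatic hypotension is redefined and orthostatic tachycardia is missing

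*SAP*

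**What the plan says.** SAP Section 9.3 says that potentially clinically relevant vital signs in the open-label phase will be listed and summarized, using the criteria in SAP Appendix 1. That appendix sits under the Section 11 heading "Potential Clinical Relevance Criteria from Protocol". The protocol's own table is Appendix 6 (Section 10.6).

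The two tables print different limits. For systolic pressure the protocol has "≥ 140 mmHg Supine < 90 mmHg" and the SAP "> 180 mmHg < 90 mmHg". For diastolic pressure the protocol has "≥ 90 mmHg Supine < 60 mmHg" and the SAP "> 105 mmHg < 50 mmHg". For orthostatic hypotension the protocol has "≥ 30 mmHg decrease in systolic blood pressure and/or a decrease of ≥ 20 mmHg in diastolic blood pressure", taken standing against supine, and the SAP has "≥ 20 mmHg decrease in systolic blood pressure and a ≥ 25 bpm increase in heart rate from supine to sitting/standing". The protocol also has an orthostatic tachycardia row, "≥ 25 bpm increase in heart rate from supine to standing", which the SAP table lacks.

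Both tables attribute their heart-rate, systolic and diastolic rows to the same FDA draft of 2/27/87. SAP Section 1 states that the SAP's methods prevail where the two documents differ. Protocol Section 9.4.2.3 promises a summary of potentially clinically relevant vital signs without naming a criteria table.

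**The concern.** A reader who trusts the heading will take the flag counts in CT-11.2.1 and CT-11.2.2 to be counts under the protocol's criteria. They are not, and the SAP neither lists nor explains a departure. Two different sets of limits citing one source also means that at least one source note is wrong, unless that draft holds two sets.

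Safety and tolerability is the trial's stated primary objective, and changes in vital signs are a named secondary safety endpoint, so the threshold for a flag matters to what is reported. Protocol Section 8.7.3 shows the tension within the plan. It excludes a subject at entry for a postural fall of at least 30 mmHg systolic or 20 mmHg diastolic, or for a diastolic pressure above 95 mmHg. On treatment, a 35 mmHg postural systolic fall without a 25 bpm heart-rate rise, or a diastolic pressure going from 80 to 100 mmHg, would not be flagged by the SAP table. This does not show which set is right, only that the two do not agree.

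The SAP table also gives no body position for its blood-pressure rows, and its orthostatic row mentions sitting, although Protocol Section 8.7.3 measures only supine and standing.

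**Working it through.** **Step 1: compare the tables rule by rule.** Inputs are Protocol Appendix 6 and SAP Appendix 1. Each heart-rate (HR), systolic (SBP) and diastolic (DBP) rule needs both a criterion value and a change from baseline.

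| Rule | Protocol | SAP | SAP against protocol |
|---|---|---|---|
| High HR, bpm | >100, rise ≥10 | >120, rise ≥15 | harder |
| Low HR, bpm | <50, fall ≥10 | <50, fall ≥15 | harder |
| High SBP, mmHg | ≥140, rise ≥20 | >180, rise ≥20 | harder |
| Low SBP, mmHg | <90, fall ≥20 | <90, fall ≥20 | same numbers |
| High DBP, mmHg | ≥90, rise ≥10 | >105, rise ≥15 | harder |
| Low DBP, mmHg | <60, fall ≥10 | <50, fall ≥15 | harder |
| Weight up | ≥7% | ≥7% | same |
| Weight down | ≥7% | ≥7% | same |
| Orthostatic hypotension | SBP fall ≥30 and/or DBP fall ≥20 | SBP fall ≥20 and HR rise ≥25 | redefined |
| Orthostatic tachycardia | HR rise ≥25 | no row | absent |

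Rules: 5 harder + 3 same + 1 redefined + 1 absent = 10. Printed HR/SBP/DBP limits that differ: HR 3 of 4, SBP 1 of 4, DBP 4 of 4, so 3 + 1 + 4 = 8 of 12.

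The count uses printed numbers only. The protocol's blood-pressure cells carry a supine label whose placement is unclear in the extracted text. If it belongs to the low limit, the low systolic row differs too and the count is 9 of 12.

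**Step 2: smallest change that is flagged.** Let *b* be the baseline, *c* the first whole value that meets the criterion, and *d* the required change. A high rule needs a rise of max(*c* − *b*, *d*); a low rule needs a fall of max(*b* − *c*, *d*). The baselines are illustrative, and position is ignored.

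| Baseline | Protocol | SAP |
|---|---|---|
| SBP 120, rise | max(140 − 120, 20) = 20 | max(181 − 120, 20) = 61 |
| DBP 80, rise | max(90 − 80, 10) = 10 | max(106 − 80, 15) = 26 |
| DBP 70, fall | max(70 − 59, 10) = 11 | max(70 − 49, 15) = 21 |
| HR 80, rise | max(101 − 80, 10) = 21 | max(121 − 80, 15) = 41 |
| HR 60, fall | max(60 − 49, 10) = 11 | max(60 − 49, 15) = 15 |

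Over ranges of baseline, protocol against SAP:
- SBP 100–135: rise of 20–40 against 46–81.
- DBP 65–85: rise of 10–25 against 21–41; fall of 10–26 against 16–36.
- HR 60–90: rise of 11–41 against 31–61.
- HR 55–80: fall of 10–31 against 15–31, with no difference from a baseline of 64 upward.

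**Step 3: test whether the orthostatic definitions are nested.** Supine-to-standing changes, illustrative:

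| SBP fall / DBP fall / HR rise | Protocol | SAP |
|---|---|---|
| 35 / 5 / 10 | hypotension | no flag |
| 10 / 22 / 10 | hypotension | no flag |
| 22 / 5 / 26 | tachycardia only | hypotension |
| 5 / 5 / 30 | tachycardia only | no flag |

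The first and third rows point in opposite directions, so neither definition of hypotension contains the other.

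**Step 4: trace the outputs.** CT-11.1 prints the criteria, CT-11.2.1 lists the flagged values and CT-11.2.2 gives their incidence. CT-11.2.3 (mean change in vital signs), CT-11.3 (body weight) and the AE tables do not use the limits.

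**The case against.** The strongest reply is that the SAP prevails, so there is no doubt about what will be programmed. No protocol passage ties Appendix 6 to the analysis: Section 9.4.2.3 names no table, and Section 8.7.3 speaks of monitoring and points to a Section 10.9 that does not exist. A monitoring table and a reporting table may legitimately differ. CT-11.1 will print the limits used. The trial is open-label with a single treatment and descriptive summaries, and its primary endpoint is AEs.

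Much of this stands as a limit on the size of the problem. It does not remove it. Precedence settles which table is run, but it does not make the heading true or supply a reason for the change. Printing the SAP's limits in CT-11.1 does not tell a reader that they depart from the protocol.

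Three further points are fair. The FDA draft is not available here, so neither source note can be called the wrong one. The protocol's own table needs care too: Section 8.7.3 defines orthostatic hypotension for eligibility within 3 minutes of standing, whereas Appendix 6 takes the reading after at least 3 minutes. Finally, the COVID-19 addendum, which the SAP says it took into account, is not among the documents, so any bearing it has cannot be checked.

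**Conclusion.** The concern holds. The SAP's vital-sign table is labelled as the protocol's and is not: 8 of 12 printed limits differ, 5 of the 10 directional rules are harder to meet, orthostatic hypotension is a different rule, and orthostatic tachycardia is dropped. On the numbers alone, those 5 rules can only give the same or fewer flags than the protocol's. Orthostatic hypotension can move either way. If the supine label restricts the protocol's low-pressure rule, a standing systolic fall from 110 to 85 mmHg is flagged only by the SAP.

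The effect is confined to CT-11.1, CT-11.2.1 and CT-11.2.2. It should be fixed before those outputs are produced, but it does not touch the primary analysis. The counts are exact and assume no distribution. The documents give no vital-sign distributions, so the change in incidence cannot be estimated. Nothing here says which limits are correct.

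**What to change.** Reconcile Protocol Appendix 6 with SAP Appendix 1 before the outputs are produced, in one of two ways:

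- **Use the protocol's criteria.** Replace SAP Appendix 1 with them, including orthostatic tachycardia and the measured positions, so that the heading is true.
- **Keep the SAP's criteria.** Correct the Section 11 heading, name each departure and state the reason. Showing incidence under both sets, separately labelled, would help readers but is optional.

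In either case:
- check the FDA source note in both tables;
- state the body position for the blood-pressure rows;
- limit the orthostatic row to positions that are measured;
- reconcile the standing time between Protocol Section 8.7.3 and Appendix 6;
- correct the pointer to Section 10.9.

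Two small operator differences can be settled at the same time: CPK above 3 times ULN in the protocol's laboratory appendix against at or above it in the SAP's, and QTcF above 450/470 msec in the protocol's ECG appendix against at or above in the SAP's.

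The cost is SAP wording and a little table programming. The protocol corrections need an amendment under Protocol Section 10.8; the pointer alone looks administrative. Reported flag counts may change in either direction, depending on the row and the body position.

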Appendix 2 Criteria for Identifying Laboratory Values of Potential Clinical Relevance

Laboratory Tests		Criteria
Chemistry		
AST (SGOT)		$\geq 3 \times$ upper limit of normal (ULN)
ALT (SGPT)		$\geq 3 \times$ ULN
Alkaline phosphatase		$\geq 3 \times$ ULN
Lactate dehydrogenase (LDH)		$\geq 3 \times$ ULN
Blood urea nitrogen (BUN)		≥ 30 mg/dL
Creatinine		≥ 2.0 mg/dL
Uric Acid		
Men		≥ 10.5 mg/dL
Women		≥ 8.5 mg/dL
Bilirubin (total)		≥ 2.0 mg/dL
Creatine phosphokinase (CPK)		$\geq 3 \times$ ULN
Prolactin		$>$ ULN
Hematology		
Hematocrit		
Men		$\leq 37\%$ and decrease of ≥ 3 percentage points from Baseline
Women		$\leq 32\%$ and decrease of ≥ 3 percentage points from Baseline
Hemoglobin		
Men		≤ 11.5 g/dL
Women		≤ 9.5 g/dL
White blood count		$\leq 2,800/\text{mm}^3$ or $\geq 16,000/\text{mm}^3$
Eosinophils		$\geq 10\%$
Neutrophils		$\leq 15\%$
Absolute neutrophil count		$\leq 1,500/\text{mm}^3$
Platelet count		$\leq 75,000/\text{mm}^3$ or $\geq 700,000/\text{mm}^3$
Urinalysis		
Protein		Increase of ≥ 2 units
Glucose		Increase of ≥ 2 units
Casts		Increase of ≥ 2 units
Additional Criteria		
Chloride		≤ 90 mEq/L or ≥ 118 mEq/L
Potassium		≤ 2.5 mEq/L or ≥ 6.5 mEq/L
Sodium		≤ 126 mEq/L or ≥ 156 mEq/L
Calcium		≤ 8.2 mg/dL or ≥ 12 mg/dL
Glucose		
Fasting		≥ 100 mg/dL
Non-Fasting		≥ 200 mg/dL
Total Cholesterol, Fasting		≥ 240 mg/dL
LDL Cholesterol, Fasting		≥ 160 mg/dL
HDL Cholesterol, Fasting		
Men		< 40 mg/dL
Women		< 50 mg/dL
Triglycerides, Fasting		≥ 150 mg/dL

Appendix 3**Criteria for Identifying ECG Measurements of Potential Clinical****Relevance**

Variable	Criterion Value ^a	Change Relative to Baseline ^a
Rate		
Tachycardia	≥ 120 bpm	increase of ≥ 15 bpm
Bradycardia	≤ 50 bpm	decrease of ≥ 15 bpm
Rhythm		
Sinus tachycardia ^b	≥ 120 bpm	increase of ≥ 15 bpm
Sinus bradycardia ^c	≤ 50 bpm	decrease of ≥ 15 bpm
Supraventricular premature beat	all	not present → present
Ventricular premature beat	all	not present → present
Supraventricular tachycardia	all	not present → present
Ventricular tachycardia	all	not present → present
Atrial fibrillation	all	not present → present
Atrial flutter	all	not present → present
Conduction		
1° atrioventricular block	PR ≥ 200 msec	increase of ≥ 50 msec
2° atrioventricular block	all	not present → present
3° atrioventricular block	all	not present → present
Left bundle-branch block	all	not present → present
Right bundle-branch block	all	not present → present
Pre-excitation syndrome	all	not present → present
Other intraventricular conduction block ^d	QRS ≥ 120 msec	increase of ≥ 20 msec
Infarction		
Acute or subacute	all	not present → present
Old	all	not present → present
		≥ 12 weeks post study entry
ST/T Morphological		
Myocardial Ischemia	all	not present → present
Symmetrical T-wave inversion	all	not present → present
Increase in QTc	QTcF ≥ 450 msec (men) QTcF ≥ 470 msec (women)	

^a In order to be identified as potentially clinically relevant, an on-treatment value must meet the “Criterion Value” and also represent a change from the subject’s baseline value of at least the magnitude shown in the “Change Relative to Baseline” column.

^b No current diagnosis of supraventricular tachycardia, ventricular tachycardia, atrial fibrillation, atrial flutter, or other rhythm abnormality.

^c No current diagnosis of atrial fibrillation, atrial flutter, or other rhythm abnormality.

^d No current diagnosis of left bundle branch block or right bundle branch block.

12 Proposed List of Summary Tables

- CT-1.1 Subject Disposition (Enrolled Sample)
- CT-1.2 Subject Disposition by Center (Enrolled Sample)
- CT-1.3 Subject Completion Rates by Week (Enrolled Sample)
- CT-1.4 Enrollment by Country (Enrolled Sample)
- CT-1.5 Enrollment by Country by Age Group (Enrolled Sample)
- CT-1.6 Summary of Proportion of the Face-to-Face and Virtual Visits by Study Week (Enrolled Sample)
- CT-2 Reasons for Discontinuation (Enrolled Sample)
- CT-3.1 Demographic Characteristics (Enrolled Sample)
- CT-3.2.1 Medical History (Enrolled Sample)
- CT-3.2.2 Psychiatric History (Enrolled Sample)
- CT-3.2.3 Borderline Personality Disorder Disease History (Enrolled Sample)
- CT-3.3 Baseline Psychiatric Scale Evaluation (Enrolled Sample)
- CT-4.1.1 Concomitant Medications: Medications Taken Prior to Start of Study Therapy (Safety Sample)
- CT-4.1.2 Concomitant Medications: Medications Taken During Study Therapy Period (Safety Sample)
- CT-4.1.3 Concomitant Medications: Medications Taken Post Study Therapy Period (Safety Sample)
- CT-4.2.1 Psychiatric Concomitant Medications: Medications Taken Prior to Start of Study Therapy (Safety Sample)
- CT-4.2.2 Psychiatric Concomitant Medications: Medications Taken During Study Therapy Period (Safety Sample)
- CT-4.2.3 Psychiatric Concomitant Medications: Medications Taken Post Study Therapy (Safety Sample)

CCI

CCI

- CT-6.1 Summary of Mean Change from Baseline in Simpson-Angus Scale (SAS) Total Score (Safety Sample)
- CT-6.2 Summary of Mean Change from Baseline in Abnormal Involuntary Movement Scale (AIMS) Total Score and Item Scores 8, 9 and 10 (Safety Sample)
- CT-6.3.1 Summary of Mean Change from Baseline in Barnes Akathisia Rating Scale (BARS) Global Clinical Assessment of Akathisia (Safety Sample)
- CT-6.3.2 Incidence of Barnes Akathisia Rating Scale (BARS) Global Clinical Assessment of Akathisia (Safety Sample)
- CT-6.4.1 Columbia-Suicide Severity Rating Scale(C-SSRS), Suicidality (Safety Sample)
- CT-6.4.2 Columbia-Suicide Severity Rating Scale(C-SSRS), Suicidal Behavior by Type (Safety Sample)
- CT-6.4.3 Columbia-Suicide Severity Rating Scale(C-SSRS), Suicidal Ideation by Type (Safety Sample)
- CT-6.4.4 Columbia-Suicide Severity Rating Scale(C-SSRS), Treatment Emergent Suicidal Behavior and Ideation (Safety Sample)
- CT-6.4.5 Columbia-Suicide Severity Rating Scale (C-SSRS) – Listing of Treatment Emergent Suicidal Ideation (Safety Sample)
- CT-6.4.6 Columbia-Suicide Severity Rating Scale (C-SSRS) – Listing of Treatment Emergent Suicidal Behavior (Safety Sample)
- CT-6.4.7 Columbia-Suicide Severity Rating Scale (C-SSRS) – Listing of Treatment Emergent Serious Suicidal Ideation (Safety Sample)
- CT-6.4.8 Columbia-Suicide Severity Rating Scale (C-SSRS) – Listing of Worsening Suicidal Ideation (Safety Sample)
- CT-7.1 Extent of Exposure to Study Medication (Safety Sample)
- CT-7.2 Number and Percentage of Subjects Receiving Study Medication and Mean and Range of Average Daily Dose (Safety Sample)
- CT-8.1 Adverse Events (All Causalities) (Safety Sample)
- CT-8.2.1 Incidence of TEAEs by System Organ Class and MedDRA Preferred Term (Safety Sample)
- CT-8.2.2 Incidence of TEAEs by System Organ Class, MedDRA Preferred Term and Severity (Safety Sample)
- CT-8.2.3 Incidence of TEAE of at Least 5% by System Organ Class and MedDRA Preferred Term (Safety Sample)
- CT-8.2.4 Incidence of TEAEs by System Organ Class and MedDRA Preferred Term, by Sex (Safety Sample)
- CT-8.2.5 Incidence of TEAEs by System Organ Class and MedDRA Preferred Term, by Race (Safety Sample)
- CT-8.2.6 Incidence of TEAEs by System Organ Class and MedDRA Preferred Term, by Age (Safety Sample)
- CT-8.2.7 Incidence of TEAEs by System Organ Class and MedDRA Preferred Term, by Region (Safety Sample)
- CT-8.2.8 Incidence of Non-Serious TEAE of at Least 5% by System Organ Class and MedDRA Preferred Term (Safety Sample)

- CT-8.2.9 Occurrence (Number of Events) of Serious Treatment-Emergent Adverse Events by System Organ Class and MedDRA Preferred Term (Safety Sample)
- CT-8.2.10 Occurrence (Number of Events) of Potentially Drug-Related Serious Treatment-Emergent Adverse Events by System Organ Class and MedDRA Preferred Term (Safety Sample)
- CT-8.2.11 Occurrence (Number of Events) of Non-Serious Treatment-Emergent Adverse Events by System Organ Class and MedDRA Preferred Term (Safety Sample)
- CT-8.3.1 Incidence of Potentially Drug-Related TEAEs by System Organ Class and MedDRA Preferred Term (Safety Sample)
- CT-8.3.2 Incidence of Potentially Drug-Related TEAEs by System Organ Class, MedDRA Preferred Term and Severity (Safety Sample)
- CT-8.4 Incidence of Deaths Due to TEAEs by System Organ Class and MedDRA Preferred Term (Safety Sample)
- CT-8.5.1 Incidence of Serious TEAEs by System Organ Class and MedDRA Preferred Term (Safety Sample)
- CT-8.5.2 Incidence of Serious TEAEs by System Organ Class, MedDRA Preferred Term and Severity (Safety Sample)
- CT-8.6.1 Incidence of TEAEs Resulting in Discontinuation from Study by System Organ Class and MedDRA Preferred Term (Safety Sample)
- CT-8.6.2 Incidence of TEAEs Resulting in Discontinuation from Study by System Organ Class, MedDRA Preferred Term and Severity (Safety Sample)
- CT-8.7.1 Incidence of TE EPS-related AEs by EPS Category and MedDRA Preferred Term (Safety Sample)
- CT-8.7.2 Incidence of Onset of Akathisia Adverse Event by Week (Safety Sample)
- CT-8.8.1 Listing of TEAEs that Are Related or Probably Related to COVID-19 (Safety Sample)
- CT-8.8.2 Listing of Serious TEAEs or Deaths that Are Related or Probably Related to COVID-19 (Safety Sample)
- CT-8.9 Incidence of Treatment-Emergent Adverse Events of Special Interests (AESIs) by System Organ Class and MedDRA Preferred Term (Safety Sample)
- CT-9.1 Listing of Deaths
- CT-9.2 Listing of Serious Adverse Events
- CT-9.3 Listing of Discontinuations Due to Adverse Events
- CT-10.1 Criteria for Laboratory Test Values with Potential Clinical Relevance
- CT-10.2.1 Listing of Laboratory Test Values with Potential Clinical Relevance by Subject (Safety Sample)
- CT-10.2.2 Listing of Laboratory Test Values with Potential Clinical Relevance by Test (Safety Sample)
- CT-10.2.3 Incidence of Laboratory Test Values with Potential Clinical Relevance (Safety Sample)
- CT-10.3.1 Mean Change from Baseline in Clinical Laboratory Test Results - Serum Chemistry (Safety Sample)
- CT-10.3.2 Mean Change from Baseline in Clinical Laboratory Test Results - Hematology (Safety Sample)
- CT-10.3.3 Mean Change from Baseline in Clinical Laboratory Test Results - Urinalysis (Safety Sample)
- CT-10.3.4 Mean Change from Baseline in Clinical Laboratory Test Results - Prolactin, by Sex (Safety Sample)
- CT-10.3.5 Mean Change from Baseline in Clinical Laboratory Test Results - Other Tests (Safety Sample)
- CT-10.4.1 Incidence of Laboratory Test Values with Potential Clinical Relevance - Prolactin (Safety Sample)
- CT-10.4.2 Listing of Laboratory Test Values with Potential Clinical Relevance - Prolactin (Safety Sample)
- CT-10.5.1.1 Incidence of Treatment-Emergent Significant Change in Lipids (Safety Sample)
- CT-10.5.1.2 Listing of Treatment-Emergent Significant Change in Lipids (Safety Sample)
- CT-10.5.2.1 Incidence of Treatment-Emergent Significant Change in Glucose (Safety Sample)
- CT-10.5.2.2 Listing of Treatment-Emergent Significant Change in Glucose (Safety Sample)
- CT-10.5.3.1 Incidence of Treatment-Emergent Metabolic Syndrome (Safety Sample)

- CT-10.5.3.2 Listing of Treatment-Emergent Metabolic Syndrome (Safety Sample)
- CT-10.6 Incidence of Potentially Liver Injury Related Laboratory Test Abnormalities (Safety Sample)
- CT-10.7 Listing of Potentially Liver Injury Related Laboratory Test Abnormalities (Safety Sample)
- CT-11.1 Criteria for Potentially Clinically Relevant Abnormalities in Vital Signs
 - CT-11.2.1 Listing of Potentially Clinically Relevant Abnormalities in Vital Signs (Safety Sample)
 - CT-11.2.2 Incidence of Potentially Clinically Relevant Abnormalities in Vital Signs (Safety Sample)
 - CT-11.2.3 Mean Change from Baseline in Vital Signs (Safety Sample)
- CT-11.3 Mean Change from Baseline in Body Weight (kg) (Safety Sample)
- CT-11.4 Mean Change from Baseline in Waist Circumference (cm) (Safety Sample)
- CT-11.5 Mean Change from Baseline in BMI (kg/m²) (Safety Sample)
- CT-12.1 Criteria for Potentially Clinically Relevant Abnormalities in ECG Evaluations
 - CT-12.2.1 Listing of Potentially Clinically Relevant Abnormalities in ECG Evaluations (Safety Sample)
 - CT-12.2.2 Incidence of Potentially Clinically Relevant Changes in ECG Evaluations (Safety Sample)
 - CT-12.2.3 Mean Change from Baseline in Electrocardiogram Results (Safety Sample)
- CT-12.3.1 Listing of Categorical Changes in QT/QTc (Safety Sample)
- CT-12.3.2 Incidence of Categorical Changes in QT/QTc (Safety Sample)
